4.5.2 Other Safety Variables

Other safety variables are listed below:

- OST examination
- OHT examination

4.5.2.1 OST Examination

This procedure will be conducted by a qualified, experienced clinical examiner. The OST examination will be accomplished by direct observation and palpation with retraction aids, as appropriate. The examination will cover the oral labial mucosa (including lips), buccal mucosa, mucogingival folds, gingival mucosa, hard palate, soft palate, tonsillar area, pharyngeal area, tongue, sublingual area, submandibular area and salivary glands. Findings from the examination will be recorded in the CRF as either normal or abnormal, with details of any abnormalities. The results of the OST examination performed at screening will be used to determine subject eligibility. Any new OST abnormality or worsening of a pre-existing condition observed by the clinical examiner or reported by the subject after the screening examination will be recorded as an AE.

Where possible, this procedure should be conducted by a single clinical examiner.

4.5.2.2 OHT Examination

This procedure should be conducted by a qualified, experienced clinical examiner. The OHT examination will be accomplished by direct observation, using retraction aids as appropriate and will identify any grossly carious lesions, signs of erosive wear, enamel irregularities, tooth fracture, gross generalized dental caries decay, decalcification and faulty restorations. The presence of any implants, fixed or removable dentures, fixed or removable orthodontic braces/bands, fixed orthodontic retainers, full crowns or veneers will be recorded. Observations

will be listed as either absent or present, and conditions noted as present will be described in the CRF. Any change observed by the clinical examiner or reported by the subject after the screening examination will be recorded as an AE.

The results of the OHT examination performed at Screening will be used to determine subject eligibility. Where possible, this procedure should be conducted by a single clinical examiner.

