10.1 Definition of an Adverse Event (AE)

An AE is any untoward medical occurrence in a clinical study subject, temporally associated with the use of a study product including any washout or lead-in product (or medical device), whether or not considered related to the study product, including any washout or lead-in product (or medical device).

NOTE: An AE can therefore be any unfavorable and unintended sign (including an abnormal laboratory finding), symptom, or disease (new or exacerbated) temporally associated with the use of a study product including any washout or lead-in product (or medical device).

Events Meeting the AE Definition:

- Any abnormal laboratory test results (hematology, clinical chemistry, or urinalysis) or other safety assessments (e.g. ECG, radiological scans, vital sign measurements), including those that worsen from baseline, considered clinically significant in the medical and scientific judgment of the investigator (i.e., not related to progression of underlying disease).
- Exacerbation of a chronic or intermittent pre-existing condition including either an increase in frequency and/or intensity of the condition.
- New conditions detected or diagnosed after study product administration even though it may have been present before the start of the study.
- Signs, symptoms, or the clinical sequelae of a suspected drug-drug interaction.
- Signs, symptoms, or the clinical sequelae of a suspected overdose of either study product or a concomitant medication. Overdose per se will not be reported as an AE/SAE unless it is an intentional overdose taken with possible suicidal/self-harming intent. Such overdoses should be reported regardless of sequelae.
- "Lack of efficacy" or "failure of expected pharmacological action" per se will not be reported as an AE. Such instances will be captured in the efficacy assessments. However, the signs, symptoms, and/or clinical sequelae resulting from lack of efficacy will be reported as AE if they fulfill the definition of an AE.

Events NOT meeting the AE definition:

- Any clinically significant abnormal laboratory findings (if applicable) or other abnormal safety assessments which are associated with the underlying disease, unless judged by the investigator to be more severe than expected for the subject's condition.
- The disease/disorder being studied or expected progression, signs, or symptoms of the disease/disorder being studied, unless more severe than expected for the subject's condition.

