- Medical or surgical procedure (e.g. endoscopy, appendectomy) is not the AE. The condition that leads to the procedure is an AE (e.g. appendicitis).

- Situations where an untoward medical occurrence did not occur (social and/or convenience admission to a hospital).
- Anticipated day-to-day fluctuations of pre-existing disease(s) or condition(s) present or detected at the start of the study that do not worsen.

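### The hard-tissue rule makes every change after screening an adverse event, including improvements and new restorations, which contradicts the protocol's own AE definition

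*SAP*

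**What the plan says.** The OHT examination takes place at screening and again at Visit 3 (schedules of activities in both documents). It covers defects such as carious lesions, tooth fracture, decalcification and faulty restorations. It also covers dental work: implants, dentures and braces, and the list ends "fixed orthodontic retainers, full crowns or veneers will be recorded". Each item is scored absent or present.

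The recording rule in SAP 4.5.2.2, identical in protocol 9.3.2, is: "Any change observed by the clinical examiner or reported by the subject after the screening examination will be recorded as an AE".

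The soft-tissue rule in SAP 4.5.2.1 and protocol 9.3.1 is narrower. It applies to "Any new OST abnormality or worsening of a pre-existing condition observed by the clinical examiner" or reported by the subject.

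Protocol 10.1 defines the event: "An AE is any untoward medical occurrence in a clinical study subject". Among the things that are not AEs it lists: "Medical or surgical procedure (e.g. endoscopy, appendectomy) is not the AE". Its next sentence adds that the condition leading to the procedure is an AE.

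The only safety endpoint is treatment-emergent AEs (protocol Table 3-1, SAP 1.2). SAP 4.5.1 counts AEs with onset from first product use onward and tabulates them by oral or non-oral class. Protocol 12.3.3 says that OHT findings themselves are only listed.

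**The concern.** The OHT rule tests neither direction nor untowardness. A site that follows it literally will put improvements and dental work on the AE page, where protocol 10.1 says they do not belong. A site that follows 10.1 will leave them off, against 9.3.2. The documents do not say which governs.

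What is at stake is the meaning of the oral AE counts. Hard-tissue findings are otherwise listed only, so the AE rule is their only route into a summary table. A record of a repaired filling would appear in Tables 14.3.1.1 and 14.3.1.2 and Listing 14.3.2.4 beside true tolerability events.

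**Working it through.** The documents state no rate or figure on this point, so the check is a comparison of rules, followed by timing and scale.

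**1. Cases under each rule**

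| Change between screening and Visit 3 | OHT rule as written | Protocol 10.1 | OHT rule with OST scope |
|---|---|---|---|
| Faulty restoration repaired (present to absent) | AE | The repair is not an AE; a defect that began before consent goes to medical history (protocol 10.3) | Not an AE |
| New crown or veneer (absent to present) | AE | Procedure is not the AE; the condition behind it is assessed | Not an AE in itself; the condition is assessed |
| Finding noted at screening, not noted at Visit 3, no treatment | AE | Nothing untoward | Not an AE |
| New fracture or new carious lesion | AE | AE | AE |
| Existing defect worsens | AE | AE (exacerbation) | AE |

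The OHT rule and 10.1 disagree in the first three rows. With OST scope they agree in all five.

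**2. Route into the endpoint**

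There is no OHT examination at Visit 2. Screening is 7 to 21 days before randomization (protocol 8.1), and Visit 3 is on Day 21 to 23 (protocol 8.2.2).

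- Shortest interval between the two examinations: 7 + 21 = 28 days.
- Longest interval: 21 + 23 = 44 days.
- Share of the interval before first product use: from 7/(7 + 23) = 23% to 21/(21 + 21) = 50%.

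A change first seen at Visit 3 may therefore have arisen before treatment. It is treatment-emergent only if its onset is placed at or after first use. SAP 4.5.1 gives no rule for dating the onset of a change found by the examiner.

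**3. Removal before lock**

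Protocol 12.3.3 and SAP 4.5.1 have all AEs reviewed before database lock. Neither gives a criterion for removing a recorded event that fails 10.1.

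**4. Scale**

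With about 53 subjects per arm, one subject moves an arm's incidence by 1/53 = 1.9 percentage points. How many subjects would be affected cannot be derived from the documents.

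**The case against.** The strongest reply is that the situation will seldom arise. Exclusion 12a removes subjects with orthodontic or prosthetic appliances or implants. Exclusion 12e removes those with dental conditions under active treatment or needing immediate treatment. Protocol 5.5.1 asks subjects to put off elective dental work. An emergency repair would often come with a reportable condition anyway, and protocol sections 10 and 10.4 make investigators responsible for events that meet the AE definition. All of this stands, and it limits the size. It does not remove the contradiction: emergency treatment is foreseen, and 9.3.2 is a direct instruction with no exception.

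A reader might go further and infer that the OST rule has the same fault, because every subject has gingivitis at entry and 10.1 excludes "The disease/disorder being studied or expected progression, signs, or symptoms of the disease/disorder being studied, unless more severe than expected". The documents do not support that. The OST rule already requires a new or worse finding. Protocol 10.1 itself counts "Exacerbation of a chronic or intermittent pre-existing condition including either an increase in frequency and/or intensity of the condition" as an AE and exempts "Anticipated day-to-day fluctuations of pre-existing disease(s) or condition(s) present or detected at the start of the study that do not worsen". Whether gingivitis is the disorder under study is not settled: every efficacy endpoint is malodor, and bleeding on probing is assessed only at screening. Moving gingival signs off the AE page could also hide local irritation by a product.

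A reader might also infer that AE counts would be loaded onto the reference arm, because stannous fluoride is expected to improve gingivitis (protocol 2.2 and 2.4). Those sections predict improvement on the experimental paste, not worsening on the reference. Improvement creates no OST adverse event in either arm.

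**Conclusion.** The point holds for the hard-tissue rule only. Protocol 9.3.2 and SAP 4.5.2.2 contradict protocol 10.1 for resolved findings and new dental work, and they differ from the OST rule without a stated reason.

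The consequence is that oral treatment-emergent AE counts can include records that are not untoward events. It is not shown that they will. That depends on such changes occurring, on sites following the rule literally, on onset being placed at or after first use, and on the pre-lock review leaving the records in. The number is unknown and probably small. The rule is the same in both arms, and the documents give no reason to expect hard-tissue changes to differ between them. The safety summaries are descriptive, so no hypothesis test and no efficacy conclusion is affected. This is a minor wording correction.

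**What to change.** In protocol 9.3.2 and SAP 4.5.2.2, replace the opening words *Any change* with *Any new OHT abnormality or worsening of a pre-existing abnormality*, and leave the rest of the sentence as it is. Both documents must change, because the SAP repeats the protocol's rule.

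Add one sentence: favourable or neutral changes, such as a resolved finding or a new crown, are recorded on the OHT page and shown in Listing 16.2.8.2, and any condition that led to a dental procedure is still assessed under protocol 10.1. Leave the OST rule unchanged.

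The cost is one wording change in each document and a line in site training. No data are lost and no assessment is added. The examiner must judge whether a change is new or worse, as the OST rule already requires.

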4.6 Analysis of Other Variables

Not applicable.

5 Changes to the Protocol Defined Statistical Analysis Plan

There were no changes or deviations to the originally planned statistical analysis specified in the protocol (Dated: 17/SEP/2022).

Appendix 1: List of Data Displays

CSR Section	TLF	Number	Title	Population	Template	Topline
14.1 Demographic Data Summary Tables and Figures						
	Table	14.1.1	Subject Disposition	All Screened Subjects	14.1.1	Yes
	Table	14.1.2	Incidence of Important protocol deviations	All randomized subjects	14.1.2	
	Table	14.1.3.1	Demographic and Baseline Characteristics	Safety Population	14.1.3.1	Yes
	Table	14.1.3.2	Demographic and Baseline Characteristics	miITT Population	14.1.3.1	
14.2 Efficacy Data Summary Tables and Figures						
	Table	14.2.1	Summary of Brushing Compliance	miITT Population	14.2.1	
	Table	14.2.2.1.1	Summary of Mean Breath Organoleptic Score	miITT Population	14.2.2.1.1	Yes
	Table	14.2.2.1.2	Summary of Mean Breath Organoleptic Score	PP Population	14.2.2.1.1	
	Table	14.2.2.2.1	Statistical Analysis of Change from Day 0 (pre-brushing) to Week 3 (pre-brushing) in Mean Breath Organoleptic Score	miITT Population	14.2.2.2.1	Yes
	Table	14.2.2.2.2	Statistical Analysis of Change from Day 0 (pre-brushing) to Week 3 (pre-brushing) in Mean Breath Organoleptic Score	PP Population	14.2.2.2.1	
	Table	14.2.3.1.1	Summary of Hydrogen Sulfide (ppb) Concentration	miITT Population	14.2.3.1.1	
	Table	14.2.3.1.2	Summary of Methanethiol (ppb) Concentration	miITT Population	14.2.3.1.1	
	Table	14.2.3.1.3	Summary of Dimethyl Sulfide (ppb) Concentration	miITT Population	14.2.3.1.1	

CSR Section	TLF	Number	Title	Population	Template	Topline
	Table	14.2.3.1.4	Summary of Total VSC (ppb) Concentration	miITT Population	14.2.3.1.1	
	Table	14.2.3.2.1	Statistical Analysis of Change from Day 0 (pre-brushing) in Hydrogen Sulfide (ppb) Concentration	miITT Population	14.2.3.2.1	Yes
	Table	14.2.3.2.2	Statistical Analysis of Change from Day 0 (pre-brushing) in Methanethiol (ppb) Concentration	miITT Population	14.2.3.2.1	Yes
	Table	14.2.3.2.3	Statistical Analysis of Change from Day 0 (pre-brushing) in Dimethyl Sulfide (ppb) Concentration	miITT Population	14.2.3.2.1	Yes
	Table	14.2.3.2.4	Statistical Analysis of Change from Day 0 (pre-brushing) in Total VSC (ppb) Concentration	miITT Population	14.2.3.2.1	Yes
	Table	14.2.3.3.1	Statistical Analysis of Change from Week 3 (pre-brushing) in Hydrogen Sulfide (ppb) Concentration	miITT Population	14.2.3.3.1	Yes
	Table	14.2.3.3.2	Statistical Analysis of Change from Week 3 (pre-brushing) in Methanethiol (ppb) Concentration	miITT Population	14.2.3.3.1	Yes
	Table	14.2.3.3.3	Statistical Analysis of Change from Week 3 (pre-brushing) in Dimethyl Sulfide (ppb) Concentration	miITT Population	14.2.3.3.1	Yes
	Table	14.2.3.3.4	Statistical Analysis of Change from Week 3 (pre-brushing) in Total VSC (ppb) Concentration	miITT Population	14.2.3.3.1	Yes
	Table	14.2.4.1	Statistical Analysis of Change from Day 0 (pre-brushing) in Mean Breath Organoleptic Score	miITT Population	14.2.4.1	Yes
	Table	14.2.4.2	Statistical Analysis of Change from Week 3 (pre-brushing) in Mean Breath Organoleptic Score	miITT Population	14.2.4.2	Yes

CSR Section	TLF	Number	Title	Population	Template	Topline
	Figure	14.2.1.1	Mean Breath Organoleptic Score (\pm SE) Plot Over Time by Study Product	miITT Population	14.2.1.1	Yes
	Figure	14.2.1.2	Mean Breath Organoleptic Score (\pm SE) Plot Over Time by Study Product	PP Population	14.2.1.1	
	Figure	14.2.2.1	Mean VSC Concentration (\pm SE) Plot Over Time by Study Product and Compound	miITT Population	14.2.2.1	
14.3 Safety Data Summary Tables and Figures						
14.3.1 Displays of Adverse Events						
	Table	14.3.1.1	Treatment Emergent Adverse Events by System Organ Class and Preferred Term	Safety Population	14.3.1.1	Yes
	Table	14.3.1.2	Treatment Emergent Adverse Events by Oral/Non-oral and Preferred Term	Safety Population	14.3.1.2	
	Table	14.3.1.3	Treatment Related Treatment Emergent Adverse Events by System Organ Class and Preferred Term	Safety Population	14.3.1.1	
	Table	14.3.1.4	Treatment Related Treatment Emergent Adverse Events by Oral/Non-oral and Preferred Term	Safety Population	14.3.1.2	
	Table	14.3.1.5	Adverse Events Related to COVID-19 by System Organ Class and Preferred Term	Safety Population	14.3.1.5	
14.3.2 Listings of Deaths, Other Serious and Significant Adverse Events						
	Listing	14.3.2.1	Death	All randomized subjects	16.2.7.1	

CSR Section	TLF	Number	Title	Population	Template	Topline
	Listing	14.3.2.2	Non-fatal Serious Adverse Events	All randomized subjects	16.2.7.1	
	Listing	14.3.2.3	Treatment Emergent Adverse Events leading to study or product discontinuation	All randomized subjects	16.2.7.1	
	Listing	14.3.2.4	Treatment Emergent Adverse Events Classified as Oral	All randomized subjects	16.2.7.1	
14.3.3 Narratives of Deaths, Other Serious and Certain Other Significant Adverse Events						
14.3.4 Other Observations Related to Safety and Abnormal Laboratory Values						
	Table	14.3.4.1	OST examination	Safety Population	14.3.4.1	
APPENDIX						
16.1.6 Listing of Subjects Receiving Test Drug(s)/Investigational Product(s) from Specific Batches, where more than one batch was used						
	NA					
16.1.7 Randomization Scheme and Codes (Subject identification and treatment assigned)						
	Listing	16.1.7.1	Randomization Information	All Randomized Subjects	16.1.7.1	
16.1.9 Documentation of Statistical Methods						
	Raw output	16.1.9.1.1	Statistical Analysis of Change from Day 0 (pre-brushing) to Week 3 (pre-brushing) in Mean Breath Organoleptic Score (Reference: Table 14.2.2.2.1)	miITT Population	SAS Output	
	Raw output	16.1.9.1.2	Statistical Analysis of Change from Day 0 (pre-brushing) to Week 3 (pre-brushing) in Mean Breath Organoleptic Score (Reference: Table 14.2.2.2.2)	PP Population	SAS Output	

CSR Section	TLF	Number	Title	Population	Template	Topline
	Raw output	16.1.9.2.1.1	Statistical Analysis of Change from Day 0 (pre-brushing) in Hydrogen Sulfide (ppb) Concentration (Reference: Table 14.2.3.2.1)	miITT Population	SAS Output	
	Raw output	16.1.9.2.1.2	Statistical Analysis of Change from Day 0 (pre-brushing in Methanethiol (ppb) Concentration (Reference: Table 14.2.3.2.2)	miITT Population	SAS Output	
	Raw output	16.1.9.2.1.3	Statistical Analysis of Change from Day 0 (pre-brushing in Dimethyl Sulfide (ppb) Concentration (Reference: Table 14.2.3.2.3)	miITT Population	SAS Output	
	Raw output	16.1.9.2.1.4	Statistical Analysis of Change from Day 0 (pre-brushing) in Total VSC (ppb) Concentration (Reference: Table 14.2.3.2.4)	miITT Population	SAS Output	
	Raw output	16.1.9.2.2.1	Statistical Analysis of Change from Week 3 (pre-brushing) in Hydrogen Sulfide (ppb) Concentration (Reference: Table 14.2.3.3.1)	miITT Population	SAS Output	
	Raw output	16.1.9.2.2.2	Statistical Analysis of Change from Week 3 (pre-brushing) in Methanethiol (ppb) Concentration (Reference: Table 14.2.3.3.2)	miITT Population	SAS Output	
	Raw output	16.1.9.2.2.3	Statistical Analysis of Change from Week 3 (pre-brushing) in Dimethyl Sulfide (ppb) Concentration (Reference: Table 14.2.3.3.3)	miITT Population	SAS Output	
	Raw output	16.1.9.2.2.4	Statistical Analysis of Change from Week 3 (pre-brushing) in Total VSC (ppb) Concentration (Reference: Table 14.2.3.3.4)	miITT Population	SAS Output	

CSR Section	TLF	Number	Title	Population	Template	Topline
	Raw output	16.1.9.3.1	Statistical Analysis of Change from Day 0 (pre-brushing) in Mean Breath Organoleptic Score (Reference: Table 14.2.4.1)	miITT Population	SAS Output	
	Raw output	16.1.9.3.2	Statistical Analysis of Change from Week 3 (pre-brushing) in Mean Breath Organoleptic Score (Reference: Table 14.2.4.2)	miITT Population	SAS Output	
16.2 Subject Data Listings						
16.2.1 Discontinued Subjects						
	Listing	16.2.1.1	Subject Disposition	All randomized subjects	16.2.1.1	
	Listing	16.2.1.2	Subject Disposition	Non-randomized subjects	16.2.1.2	
16.2.2 Protocol Deviations						
	Listing	16.2.2.1	Important Protocol Deviations	All randomized subjects	16.2.2.1	
	Listing	16.2.2.2	All Protocol Deviations	All randomized subjects	16.2.2.2	
16.2.3 Patients Excluded from the Efficacy Analysis						
	Listing	16.2.3.1	Exclusions from Analysis Populations	All randomized subjects	16.2.3.1	
16.2.4 Demographic Data						

CSR Section	TLF	Number	Title	Population	Template	Topline
	Listing	16.2.4.1	Demographic and Baseline Characteristics	All randomized subjects	16.2.4.1	
	Listing	16.2.4.2	Medical History and Current Medical Conditions	All randomized subjects	16.2.4.2	
	Listing	16.2.4.3	Prior medications	All Screened subjects	16.2.4.3	
	Listing	16.2.4.4	Concomitant medications and significant non-drug therapies taken during treatment	All randomized subjects	16.2.4.4	
16.2.5 Compliance and/or Drug Concentration Data (if available)						
	Listing	16.2.5.1	Brushing Compliance	All randomized subjects	16.2.5.1	
	Listing	16.2.5.2	Supervised Brushing	All randomized subjects	16.2.5.2	
16.2.6 Individual Efficacy Response Data						
	Listing	16.2.6.1	Breath Organoleptic Score Data	All randomized subjects	16.2.6.1	
	Listing	16.2.6.2	VSC Concentration Data	All randomized subjects	16.2.6.2	
16.2.7 Adverse Event Listings						
	Listing	16.2.7.1	Adverse Events	All randomized subjects	16.2.7.1	Yes

CSR Section	TLF	Number	Title	Population	Template	Topline
	Listing	16.2.7.2	Adverse Events	Non-randomized subjects	16.2.7.1	
	Listing	16.2.7.3	All Adverse Events Related to COVID-19	All Screened subjects	16.2.7.1	
	Listing	16.2.7.4	Incidents	All Randomized Subjects	16.2.7.4	
16.2.8 Other Listings and Listing of Laboratory Measurements, when required by regulatory authorities (if applicable)						
	Listing	16.2.8.1	Oral Soft Tissue examination	All randomized subjects	16.2.8.1	
	Listing	16.2.8.2	Oral Hard Tissue examination	All randomized subjects	16.2.8.2	
16.4 Individual Subject Data Listings						
	NA
